5.6 Follow-Up for Subject Withdrawal from Study

In order to minimize missing data for efficacy and safety assessments, subjects who prematurely discontinue study drug treatment should continue to be followed for all regularly scheduled visits, unless they have decided to discontinue the study participation entirely (withdrawal of informed consent). Subjects should be advised on the continued clinical importance of their data even if they discontinue treatment with study drug early.

If, during the course of study drug administration, the subject prematurely discontinues (D/C) study participation, the procedures outlined for the applicable Premature D/C Visit in the Schedule of Events

(Appendix A) should be completed. Ideally, this should occur on the day of study drug discontinuation, but no later than 2 days after their final dose of study drug and prior to the initiation of any other anti-HCV therapy. However, these procedures should not interfere with the initiation of any new treatments or therapeutic modalities that the investigator feels are necessary to treat the subject's condition. Following discontinuation of study drug, the subject will be treated in accordance with the investigator's best clinical judgment. All attempts must be made to determine the date of the last study drug dose and the primary reason for discontinuation of study drug or study participation. The last dose of any study drug and reason for discontinuation will be recorded in the eCRF.

If a subject is discontinued with an ongoing adverse event or an unresolved laboratory result that is significantly outside of the reference range, the investigator will attempt to provide follow-up until a satisfactory clinical resolution of the laboratory result or adverse event is achieved.

5.7 Study Drug

5.7.1 Identity of Study Drug

Information about the study drug to be used in this study is presented in Table 2.

Table 2: Identity of Study Drug

Study Drug	Manufacturer	Mode of Administration	Dosage Form	Strength
Glecaprevir/pibrentasvir	AbbVie	Oral	Film-coated tablet	100 mg/40 mg

Three tablets of GLE/PIB combination will be taken daily and should be taken at the same time each day. The study drug must be taken with food.

Glecaprevir/pibrentasvir combination tablets will be provided.

5.7.2 Packaging, labelling, storage and accountability of clinical trial supplies

Glecaprevir/pibrentasvir will be provided by AbbVie and should be dispensed under the supervision of the investigator or a qualified member of the study team including drug treatment center staff, or by a hospital/clinic pharmacist.

Participants will not be required to return any unused study drug. Study drug may not be relabeled or reassigned for use by other participants.

A designated person at the study site must receive the study drug shipment. That person must check that the supplies are in good condition and are complete as per the shipping records. Study drugs must be stored in a secure location with limited access. The study drug must only be dispensed according to the protocol and records must be kept detailing supplies received, dispensed to the participant, returned from the participant and returned to the sponsor or destroyed at site, as applicable. Study staff must not open or count clinical trial supplies prior to dispensing.

Study drug should be stored in a securely locked area, accessible only to authorized site personnel. To ensure the stability of the study drug and to ensure proper product identification, the drug product should not be stored in a container other than the container in which they are supplied.

Glecaprevir/pibrentasvir should be stored according to the product label.

Participants should ensure that the study drug is stored securely away from children and in dry conditions. The study drug should be kept in the original packaging.

5.8 Protocol Deviations

The Investigator is responsible for complying with all protocol requirements, written instructions and applicable laws regarding protocol deviations. Protocol deviations are prohibited except when necessary to eliminate an immediate hazard to study subjects. If a protocol deviation occurs (or is identified), the Investigator is responsible for notifying IRB, regulatory authorities (as applicable) and the Sponsor.

5.9 Study Labs

The study-specific laboratory tests being conducted are HCV RNA, complete blood count (CBC), comprehensive metabolic panel (CMP), hepatitis B surface antigen (HBsAg), urine drug testing, and urine/serum beta HCG. These tests are able to be submitted to the study site's local laboratory of choice.

The chemistry tests required in the CMP are alanine aminotransferase (ALT/SGPT); albumin:globulin (A:G) ratio; albumin, serum; alkaline phosphatase, serum; aspartate aminotransferase (AST/SGOT); bilirubin, total; BUN; BUN:creatinine ratio; calcium, serum; carbon dioxide, total; chloride, serum; creatinine, serum; eGFR calculation; globulin, total; glucose, serum; potassium, serum; protein, total, serum; sodium, serum.

The drug screen analytes required in the urine drug test are amphetamine; barbiturate; benzodiazepines; cocaine or benzoylecgonine; fentanyl; methadone; opiates; oxycodone/oxymorphone; phencyclidine (PCP); propoxyphene; tramadol.

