3.3 Secondary Endpoints

- 1) HCV treatment completion: Proportion of those initiating treatment who complete HCV treatment defined as taking more than 90% of prescribed treatment course by expected end of treatment date.
- 2) SVR 12: Proportion of participants with HCV RNA <15 IU/ml between 10 and 36 weeks after end of treatment in each randomization arm.
- 3) Time to HCV treatment initiation after randomization.

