7.3.3 Secondary outcomes

- 1) HCV treatment completion: Proportion of those initiating treatment who complete HCV treatment defined as taking more than 90% of prescribed treatment course by expected end of treatment date.
- 2) SVR 12: Proportion of participants with HCV RNA <15 IU/ml between 10 and 36 weeks after end of treatment in each randomization arm.

Analysis for secondary outcomes 1 and 2 will be logistic regression analyses.

- 3) Time to HCV treatment initiation after randomization.

For secondary outcome 3, a time to event outcome, we will perform survival (Kaplan Meier) analysis for time to HCV treatment initiation.

Analysis of adverse event data will primarily be descriptive. Adverse event data will be compared between randomization arms using Fisher's exact Test.

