APPENDIX A. SCHEDULE OF EVENTS (ALL PARTICIPANTS)

	Recruitment Screen	Day 0	Treatment Day 1	Treatment Week 4	End of Treatment -0d/+30d	Post-Treatment Week 12 -14d/+30d	Post-Treatment Week 24 -14d/+30d	Post-Treatment Week 36 -14d/+30d	Early D/C Visit
Eligibility Review ^a	X	X							
Vital Signs ^b		X							
Demographics		X							
Medical History		X							
Concomitant Medications ^c		X			X				
Randomization		X							
Referral to HCV Treatment (SOC Arm Only)		X							
AE/SAE Collection ^d			→	→	→				
Laboratory Testing									
HBsAg		X							
Pregnancy Test ^e		X							
CBC ^f		X							
HCV RNA ^g		X			X	X		X	X
CMP		X			X	X			X
Urine Toxicology Screen		X			X	X	X	X	
Dried Blood Spot		X			X	X	X	X	X
Surveys/Questionnaires									
Study Survey		X			X	X	X	X	
PRO/QOL Measures		X			X	X	X	X	
Intervention Arm Only									
Peer Contact ^h		X	→	→	→	→			X
Study Drug Dispensation ⁱ			X	X					

^aIncluding documentation of HCV infection (antibody) and treatment history.

^bIncluding height, weight, temperature, pulse, respiratory rate, and blood pressure.

^cAll medication (including supplements and over-the-counter) will be collected.

^dAE/SAE collection starts with initiation of DAAs, continues through 30 days after last DAA dose.

^eFor all participants of childbearing potential. Urine or serum test.

^fWith or without differential.

^gCLIA certified.

^hPeer contact to occur weekly and as needed between visits until SVR 12. Contact can be in-person, via phone, or video.

ⁱStudy drug can be dispensed in smaller amounts more frequently if participant is unable to maintain 4-week supply at home.

APPENDIX B. SCHEDULE OF EVENTS (PARTICIPANTS WHO DO NOT START HCV TREATMENT BY WEEK 12 AFTER RANDOMIZATION IN EITHER ARM)

For participants who have not initiated treatment by Week 12 after randomization, complete the following.

	Week 12 after randomization -14d/+30d	Week 24 after randomization -14d/+30d	Week 36 after randomization -14d/+30d	Week 56 after randomization -14d/+30d
Laboratory Testing				
Urine Toxicology Screen	X	X	X	X
Dried Blood Spot	X	X	X	X
HCV RNA ^e		X		X
Surveys/Questionnaires				
Study Survey	X	X	X	X
PRO/QOL Measures	X	X	X	X
Rescreen for SOC Participants to Rollover to Intervention Arm				
Eligibility Review		X		
Vital Signs ^a		X		
Concomitant Medications ^b		X		
HBsAg		X		
Pregnancy Test ^c		X		
CBC ^d		X		
CMP		X		
Peer Contact ^f		→		

^aIncluding height, weight, temperature, pulse, respiratory rate, and blood pressure.

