^bAll medication (including supplements and over-the-counter) will be collected.

^cFor all participants of childbearing potential. Urine or serum test.

^dWith or without differential.

^eCLIA certified.

^fParticipant will meet with peer on date of rescreen. If participant is still eligible for rollover to Intervention Arm after rescreening labs result, peer contact to occur weekly and as needed between visits until SVR 12. Contact can be in-person, via phone, or video.

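### The post-treatment Week 24 visit lies wholly inside the SVR12 window but draws no HCV RNA, so a missed Week 12 draw may leave SVR12 missing

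*Combined protocol and SAP*

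**What the plan says.** Section 3.3 defines the SVR12 endpoint as "Proportion of participants with HCV RNA <15 IU/ml between 10 and 36 weeks after end of treatment in each randomization arm". Section 7.3.3 repeats the definition and adds "Analysis for secondary outcomes 1 and 2 will be logistic regression analyses". The endpoint is tied to time since end of treatment, not to a named visit.

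Appendix A sets three visits after end of treatment, headed "Post-Treatment Week 12 -14d/+30d", "Post-Treatment Week 24 -14d/+30d" and "Post-Treatment Week 36 -14d/+30d". Its HCV RNA row is marked at Day 0, End of Treatment, Post-Treatment Weeks 12 and 36, and the early discontinuation visit. It is blank at Week 24. The row "Dried Blood Spot" is marked at Week 24, as are urine toxicology, the study survey and the PRO/QOL measures.

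Section 5.9 begins "The study-specific laboratory tests being conducted are HCV RNA, complete blood count (CBC), comprehensive metabolic panel (CMP), hepatitis B surface antigen (HBsAg" and goes on to urine drug testing and beta HCG. It does not mention the dried blood spot, and no other section says what the spot is tested for.

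Section 7.3.4 expects little missing data and plans multiple imputation as a sensitivity analysis. No section says how a participant without an SVR12 result is scored.

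**The concern.** The wide SVR12 period looks intended to accept results obtained later than Week 12. The schedule makes little use of it. A participant who misses the Week 12 draw and comes at Week 24 is seen inside the period and gives other samples, but is not tested for the endpoint. The next scheduled HCV RNA is at Week 36, and that visit may be held after the endpoint period has closed.

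Cure is half of the clinical hypothesis in Section 2.2, and SVR12 is the endpoint that measures it. At stake are avoidable missing results in a secondary endpoint of a 124-person trial. The primary endpoint, treatment initiation, is not affected.

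**Working it through.** The plan gives no figure for missing SVR12 results, so there is none to reproduce. Its power figure (85%, Section 7.3.1) concerns the primary endpoint and does not enter here.

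**Windows, in days after end of treatment (both end days counted)**

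- SVR12 period: 10 × 7 = 70 to 36 × 7 = 252.
- Week 12 visit: 84 − 14 = 70 to 84 + 30 = 114. All 45 days are inside; HCV RNA is drawn.
- Week 24 visit: 168 − 14 = 154 to 168 + 30 = 198. All 45 days are inside; HCV RNA is not drawn.
- Week 36 visit: 252 − 14 = 238 to 252 + 30 = 282. Days 238 to 252 are inside, which is 15 of 45; the other 30 are too late.

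The End of Treatment draw (days 0 to 30) comes before the period opens. If post-treatment weeks were counted from an End of Treatment visit held 30 days late (an assumption), Week 24 would run from day 184 to 228, still 45 of 45 inside. Week 36 would run from day 268 to 312, with 0 of 45 inside.

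**Size**

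From Section 7.3.1: 62 per arm, with planned initiation of 70% and 40%. Starters: 62 × 0.70 + 62 × 0.40 = 43.4 + 24.8 = 68.2. The primary endpoint counts starts within 12 weeks of randomization, so on the planning rates these are Appendix A participants.

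Assumptions, not in the documents: a share *m* = 20% miss the Week 12 draw; a share *a* = 70% of them attend each later visit, independently; a share *f* of Week 36 visits falls on or before the target day.

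- Missing Week 12: 68.2 × 0.20 = 13.64.
- Lost as written: 13.64 × (1 − *a* × *f*).
- Lost with a Week 24 draw: 13.64 × (1 − *a*) × (1 − *a* × *f*).

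| Week 36 timing | *f* | Lost as written | Lost with Week 24 draw |
|---|---|---|---|
| All on or before target day | 1 | 13.64 × 0.30 = 4.09 | 4.09 × 0.30 = 1.23 |
| Uniform over the window | 15/45 | 13.64 × 0.767 = 10.46 | 10.46 × 0.30 = 3.14 |
| All after target day | 0 | 13.64 | 13.64 × 0.30 = 4.09 |

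With uniform timing, a miss rate of 10% gives about 5 lost against 2, and 30% gives about 16 against 5. Among Week 12 missers who do attend Week 36, the share without a scheduled result is 0%, 67% or 100% across the three timing rows.

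**The case against.** The case against rests on four points.

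- **Recovery outside the schedule.** Because SVR12 is defined by time, a Week 12 draw taken late, up to week 36, still counts. Section 2.1 notes that many patients attend their program several times a week, and Section 4.2.12 allows samples to be taken at those visits. In the standard-of-care arm, Section 4.2.9 has staff collect progress from the referral site. This stands and lowers the loss. But no HCV RNA is scheduled between day 114 and day 238, Section 5.8 bars deviations except for an immediate hazard, and the referral-site route covers one arm with no stated test or timing.
- **Who misses Week 12.** The model lets missers attend Week 24 at 70% whatever their reason for missing. Section 7.1 expects 10% loss to follow-up, and a Week 24 draw recovers nothing from those who are lost. This stands.
- **Overlap with the end of the window.** Part of the loss comes from the Week 36 visit running past week 36. If every Week 36 draw counted, the gain would fall from about 7 results (10.46 − 3.14) to about 3 (4.09 − 1.23). This stands too, but the gain is not zero.
- **The dried blood spot.** It may be intended for HCV RNA. Section 5.9 speaks of tests sent to local laboratories, so its silence does not prove that the spot goes untested. The spot can be neither counted as a fallback nor ruled out.

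A reader might also infer that the gap favors test and treat, since only that arm has weekly peer contact up to SVR 12. The documents do not support a direction. They give no missingness by arm and no rule that scores missing as failure; participants may decline peer services; and referral-site data could offset the imbalance. Suppose 95% cure, missing scored as failure and uniform Week 36 timing, all assumed. The true difference is then (0.70 − 0.40) × 95 = 28.5 points. Missing 10% against 25% of Week 12 draws gives an observed difference of 30.7; equal 20% missingness gives 24.1. The sign changes with the assumption.

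**Conclusion.** The schedule gap is real: Week 24 is a planned visit wholly inside the SVR12 period with no HCV RNA, and the one later scheduled draw counts on a third of its allowed days. A missed Week 12 draw may therefore leave SVR12 missing in a participant who was seen in time.

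It is tempting to conclude that most participants who miss Week 12 lose their result. That does not follow. Two thirds of Week 36 attenders is the figure for uniform timing only; the possible range is 0 to 100%, and results obtained outside the schedule would still count.

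Under the stated assumptions (68 starters, 20% missing Week 12, 70% attending later visits), the loss is about 4 to 14 results as written and about 1 to 4 with a Week 24 draw. Among missers who attend Week 24, the draw secures a result however Week 36 visits are timed. This is a cheap improvement to a secondary endpoint, not an error in the plan.

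**What to change.** In Appendix A, add a conditional HCV RNA at Post-Treatment Week 24, in both arms, with a footnote limiting it to participants who have no HCV RNA result from post-treatment week 10 onward. If the dried blood spot taken at that visit is to be tested for HCV RNA, name the assay in Section 5.9 and state whether its result counts for SVR12.

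The cost is one schedule cell and a footnote. Each added test stands in for a Week 12 test that was planned but not done, at a visit that already exists. The downside is one extra blood draw at Week 24 for those participants.

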6 SAFETY CONSIDERATIONS

6.1 Known and Potential Risks to Participants

6.1.1 Collection of Blood

Collection of blood may cause slight discomfort, pain, bleeding or bruising at the collection site. Rarely, fainting or infection may occur. Only properly trained clinical staff will draw blood. The amount of blood collected is the minimal amount for proper analysis.

6.1.2 Internet-Based Data Collection

Data collection will be performed using the REDCap electronic data collection (EDC) and storage hosted by Johns Hopkins University. All data in REDCap will be de-identified. Each site will maintain a record of which participant corresponds to participant numbers assigned by REDCap. This file will be password protected if electronic or kept in a locked location if in the participant binder. Only authorized personnel requiring a password will be permitted to enter data. There is risk, although minimal, of unauthorized persons obtaining confidential information.

In brief, the REDCap Consortium consists of 84 institutional partners from CTSA, GCRC, RCMI and other institutions, in which JH is an active participant. It was developed by CTSA partners at Vanderbilt, with the goal of enabling investigator research through the establishment of a more user-friendly database system. This consortium supports two secure web-based applications designed to enable data capture for research studies. The software contains an intuitive interface for collecting data with data validation commands, allows for automated export procedures to statistical packages (e.g. SAS) and provides advanced features that allow for branching logic, file uploading, etc. The system itself is supported on MySQL, an open source database similar to SQL/Oracle, and operates on a web-based system. All servers are backed-up at each data center (institution) and include password protection to provide enhanced security while maintaining accessibility via the internet.

6.2 Complaints and Adverse Events

6.2.1 Data safety monitoring

This study implements on-label use of the medication GLE/PIB for persons with Hepatitis C Virus whose current infection has not been exposed to prior direct-acting antiviral (DAA) therapy. There are not expected to be changes to the known safety and efficacy data for this agent. Thus, there will be no formal data safety monitoring board. The site investigator will determine grade (Division of AIDS (DAIDS) Table for Grading the Severity of Adult and Pediatric Adverse Events) and relatedness to GLE/PIB for all adverse events and if any serious unexpected adverse events arise, the site investigator will discuss and decide with the study Principal Investigator whether this protocol should be suspended.

6.2.2 Medical Complaints/Adverse Events and Serious Adverse Events

An AE is defined as any untoward medical occurrence in a subject or clinical investigation subject administered a pharmaceutical product and which does not necessarily have a causal relationship with this treatment. An AE can therefore be any unfavorable and unintended sign (including an abnormal

laboratory finding), symptom, or disease temporally associated with the use of a medicinal (investigational) product, whether or not the event is considered causally related to the use of the product.

An AE can result from use of the drug as stipulated in the protocol or labeling, as well as from accidental or intentional overdose, drug abuse, or drug withdrawal. Any worsening of a pre-existing condition or illness is considered an AE. Worsening in severity of a reported AE should be reported as a new AE. Laboratory abnormalities and changes in vital signs are considered to be AEs only if they result in discontinuation from the study, necessitate therapeutic medical intervention, meets protocol specific criteria (see Section 6.3 regarding toxicity management) and/or if the investigator considers them to be AEs.

Adverse event reporting will follow the requirements outlined below. Adverse events will also be recorded and tracked in a safety monitoring database by the investigators. Serious adverse events (SAEs) will be reported to the Institutional Review Board according to IRB guidelines and to AbbVie via the Johns Hopkins University Transplant Oncology and Infectious Diseases Clinical Research Center (TOID CRC).

All Grade 3 or higher and all SAEs related to the use of GLE/PIB in intervention arm or prescribed DAA course in SOC arm will be collected. Thus, AEs and SAEs will only be collected from the time of first DAA dose to 30 days after completion of DAA course.

All Grade 3 or higher AEs and all SAEs will be reviewed by the principal investigator as they occur in a timely manner. All AEs related or possibly related to GLE/PIB will be reported by the site to the TOID CRC within 72 hours of the site being made aware via the REDCap EDC system. All SAEs will be reported to the TOID CRC via the REDCap EDC system within 24 hours of the site being made aware. Notification of all SAEs will be made to AbbVie by the TOID CRC via email within 24 hours of entry into REDCap.

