3.4 Exploratory Endpoints

- 1) Impact of test and treat versus standard of care referral on proportion of participants with change in substance use assessed by self-reported drug use in the preceding 30 days and urine toxicology at recruitment screening, end of HCV treatment, and post-treatment weeks 12, 24, and 36. Participants who do not start HCV treatment will be assessed at weeks 12, 24, and 36 post-randomization.
- 2) Impact of test and treat versus standard of care referral on subsequent substance use disorder treatment engagement-Proportion of expected weekly OTP visits actually attended, based on participant's OTP treatment plan.
- 3) Proportion of patients in the standard of care arm who are not offered treatment within 6 months (24 weeks) of randomization.
- 4) Proportion of patients in the standard of care arm who do not initiate treatment within 6 months (24 weeks) of randomization and subsequently initiate HCV treatment after study cross over to intervention arm.
- 5) Patient reported outcomes, quality of life measures, and patient satisfaction with test and treat model versus standard of care referral will also be assessed.
- 6) Proportion of participants with grade 3 or greater adverse events (AEs) in test and treat model versus standard of care referral.

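### Section 6.2.2 conflicts with itself and with exploratory endpoint 6 on which Grade 3+ adverse events are collected, and the endpoint has no stated denominator that fits the collection window

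*Combined protocol and SAP*

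**What the plan says.** **Endpoint and analysis.** Section 3.4, exploratory endpoint 6, is the "Proportion of participants with grade 3 or greater adverse events (AEs) in test and treat model versus standard of care referral", with no mention of relatedness or of treated participants only. Section 7.3.3 calls the AE analysis primarily descriptive and then adds: "Adverse event data will be compared between randomization arms", by Fisher's exact test. Section 7.2 puts every analysis on the modified intention-to-treat (mITT) population and defines no safety population.

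**Collection.** Section 6.2.2 gives the scope as "All Grade 3 or higher and all SAEs related to the use of GLE/PIB in intervention arm or prescribed DAA course in SOC arm". It then draws a consequence: "AEs and SAEs will only be collected from the time of first DAA dose to 30 days after completion of DAA course". Its 72-hour REDCap route is for AEs related or possibly related to GLE/PIB.

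**Text pointing to wider capture.**
- Section 6.2.2 defines an AE "whether or not the event is considered causally related to the use of the product".
- Section 6.2.2 also states: "All Grade 3 or higher AEs and all SAEs will be reviewed by the principal investigator as they occur in a timely manner".
- On serious events, section 6.2.2 states: "All SAEs will be reported to the TOID CRC via the REDCap EDC system within 24 hours of the site being made aware". Section 8.4.3 has the coordinating center confirm seriousness and attribution.
- Section 6.2.1 has the site investigator grade every AE and judge its relatedness.
- Section 6.2.3 has all Grade 3 and 4 events evaluated, for medical management, and provides a category for events without a reasonable causal possibility.
- Footnote d of Appendix A limits AE collection by time only.

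**The concern.** The one sentence that sets the scope of collection is narrower than the endpoint it has to feed. A site that follows it could properly leave out a non-serious Grade 3+ event that it considers unrelated, although endpoint 6 counts that event. Another of the five programs, relying on the review sentence, could record the same event. The by-arm proportion would then depend partly on how each site read the section.

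Where the narrow reading is applied, the filter is a judgement made without blinding. In the referral arm it concerns a DAA course given off site, which may or may not be GLE/PIB. Attribution could therefore differ by arm.

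A second mismatch does not depend on relatedness. AE data exist only after a first DAA dose, and starting a DAA is what the intervention is meant to change. An mITT proportion would count people who were never under AE observation as free of events, and there would be more of them in the referral arm.

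**Working it through.** **1. Event scope, text against text.** The question is whether each class of event is certain to reach the database.

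| Event after first DAA dose | Collection sentence, literal reading | Other text | Result |
|---|---|---|---|
| SAE, related | collected | all SAEs reported (6.2.2, 8.4.3) | captured |
| SAE, unrelated | not collected | all SAEs reported; attribution confirmed centrally | captured, against the collection sentence |
| Non-serious Grade 3+, related | collected | 72-hour REDCap route (names GLE/PIB) | captured |
| Non-serious Grade 3+, unrelated | not collected | reviewed and evaluated, but no explicit REDCap route | unsettled |

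The sentence can also be parsed so that relatedness qualifies SAEs only. That gives all-cause Grade 3+ AEs but only related SAEs, which contradicts the all-SAE reporting rule. The sentence needs correcting under either parse.

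**2. The plan's own figure (section 7.3.1).** The inputs are 70% and 40% initiation, two-sided alpha 0.05, 85% power and about 10% dropout. The continuity-corrected two-proportion formula gives 55 per arm, and 55 / 0.90 = 61.1, rounded up to 62 per arm or 124 in total. Power at 55 per arm is 85.5% with the correction and 84.6% by exact Fisher. The plan's figures reproduce, so its uptake rates and arm sizes are used below. The AE point does not depend on the power calculation.

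**3. Who falls under AE collection, at 62 per arm.**
- Test and treat: 62 × 0.70 = 43.4 start; 62 − 43.4 = 18.6 do not.
- Referral: 62 × 0.40 = 24.8 start; 62 − 24.8 = 37.2 do not.
- With referral uptake at 30% or 50%, the ends of the plan's range, 43.4 or 31.0 referral participants do not start.

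**4. What an mITT proportion would show.** Let *q* be the Grade 3+ risk among treated participants, assumed equal in both arms. The expected mITT proportions are 0.70*q* and 0.40*q*, with ratio 0.70 / 0.40 = 1.75. The ratio is 0.70 / 0.50 = 1.40 at 50% referral uptake and 0.70 / 0.30 = 2.33 at 30%.

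The documents give no value for *q*. Assumed values:

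| *q* | Test and treat | Referral |
|---|---|---|
| 5% | 3.5% | 2.0% |
| 10% | 7.0% | 4.0% |
| 20% | 14.0% | 8.0% |

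**5. Effect of a relatedness filter.** If a share *r* of these events is judged related, equal in both arms, each proportion is multiplied by *r*. With *q* = 10% and *r* = 25% (both assumed), the result is 1.75% against 1.00%. The ratio is unchanged, but a different quantity is being measured.

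Steps 3 to 5 use the plan's initiation rates, which serve an endpoint measured at 12 weeks. They leave out participants who start later or roll over after week 24.

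**The case against.** The strongest reply is that the plan as a whole does not intend a related-only collection. Five places point the other way: the AE definition, the review sentence, the all-AE relatedness judgement in 6.2.1, the category for unrelated events in 6.2.3, and the Appendix A footnote. This stands in part. A reader might infer that the collected data cannot produce endpoint 6, but the documents do not go that far. They contradict each other, and the outcome depends on which sentence a site follows.

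A reader might also infer that an SAE judged unrelated on site would go unrecorded and unchecked. The documents do not support that. Sections 6.2.2 and 8.4.3 send all SAEs to the coordinating center, which confirms attribution.

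Nor does the word introducing the collection window prove that relatedness is the filter. The window also follows from the AE definition, which presupposes that a product has been given.

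Finally, the AE analysis is primarily descriptive, the endpoint is exploratory and GLE/PIB use is on label. Wider capture would not make the Fisher test informative either. Among starters, 2/43 against 1/25 gives p = 1.0, and 4/43 against 3/25 gives p = 0.70 (illustrative counts). This is correct. The gain from a change is a well-defined endpoint, not power.

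**Conclusion.** The point holds as an internal contradiction. Section 6.2.2 does not settle whether non-serious, unrelated Grade 3+ AEs are collected, while endpoint 6 and the Fisher comparison count them. How many events this affects cannot be estimated from the documents.

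The denominator problem is firmer, because it applies under either reading. At planned uptake about 19 of 62 test-and-treat and 37 of 62 referral participants would have no AE data. An mITT comparison would then show a ratio of 1.75 (1.40 to 2.33 over the plan's range of referral uptake) with no difference in risk among those treated. This assumes equal risk among treated participants, the plan's uptake rates, and no late starts or rollover. The consequence is confined to safety reporting.

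**What to change.** - **Scope (6.2.2).** State that all Grade 3+ AEs and all SAEs are collected regardless of relationship, within the existing window. Record relationship as a separate field using the two categories in 6.2.3. Bring the 72-hour route, 6.2.1 and the Appendix A footnote into line.
- **Denominator (3.4, 7.2, 7.3.3).** Report endpoint 6 among DAA-treated participants, as a stated exception to mITT, with related events as a subset. This is a comparison of people selected by starting treatment, so it should be presented descriptively.
- **Rollover.** State how events are counted in referral participants who start a DAA after crossing over.
- **If related-only collection is kept,** rename endpoint 6 to DAA-related Grade 3 or greater AEs among treated participants.

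The cost is protocol wording, a few more AE entries in REDCap, and some added follow-up with off-site referral providers to obtain unrelated events.
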